20.0 Compensation for Research-Related Injury

As included in the attached consent form, if the subject develops an illness or sustains an injury due to the research study, the study sponsor (Reia, LLC) will pay for the reasonable costs of medical treatment. The sponsor will not pay for:

- Treatment of illness or injury that results from the negligence of a health care provider, or
- Treatment of a condition the subject had before they were in the study.

The sponsor will not offer any other payments for study-related illness or injury such as lost wages, expenses other than medical care, or pain and suffering.

21.0 Economic Burden to Subjects

Participation in this study should not lead to additional cost for the subjects. Laboratory testing will not be performed, nor are there reasonably anticipated events which will require additional care or follow up. Since participation will happen at the time of routine care, there will not be additional travel expenses incurred.

22.0 Consent Process

Process of Consent

Each subject who presents for a study visit will be shown to a private room by a member of the clinical research unit or a member of the clinical study team. The purpose of the study will be reviewed, and if the subject continues to be interested in participation, then study eligibility will be confirmed, and the informed consent process will begin. Each subject will be given a copy of the consent form. Based on their preference, the form will be read to them aloud or they can read it independently. Each section will then be summarized; questions will be encouraged and answered fully. The subject will then be asked to teach back the information presented in that section to ensure comprehension before moving on to the next section.

The consent document will then be signed and dated by the subject providing consent and the person obtaining consent. A copy of the consent document will be scanned into the subject's medical record and a copy will be given to the subject. The original will be kept in the locked cabinet with other research documents.

As part of the process, subjects will be given as much time as they need to decide on participation. If they appear to be feeling pressure or need more time, they will not be enrolled in the study. If at any point the subject indicates she does not want to take part in the research, the informed consent process will be stopped.

Subject Capacity

Potential subjects for recruitment to this study are known to the FPMRS clinical team and their baseline capacity is known. The subject will not be entered into the study if there is concern regarding capacity to provide consent based on a change in function from previous encounters, or any of the following:

- A diagnosis of dementia or cognitive impairment.
- History of an evaluation of dementia since the last encounter in the FPMRS clinic.
- A report, in medical records or from a family member or person well acquainted with the subject, that the subject has symptoms of cognitive impairment or dementia.

- An abnormal degree of confusion, forgetfulness, or difficulties in communication that is observed in the course of interacting with the subject.
- Psychotic symptoms, bizarre or abnormal behavior exhibited by the subject.

Subject Comprehension

As described above, after the subject has read or been read the consent document, each section will again be verbally reviewed and summarized. In this step, comprehension will be determined by a "teach back" method.

23.0 Process to Document Consent in Writing

Consistent with the standard operating procedure: *Written Documentation of Consent* (*HRP-091*) of the *D-HH Human Research Protection Program* (local IRB), the informed consent process will begin when the subject agrees to take part in the study and end when the consent process is documented in writing. The consent form (see attached) has been written in understandable language and has signature blocks for the printed name, signature and date for both the subject and the person obtaining consent (the principle investigator, co-investigator, research assistant, or coordinator). The subject will receive either a photo copied version or a second signed version of the consent form.

24.0 Setting

The study will take place at Dartmouth-Hitchcock Medical Center in the Faulkner Ambulatory Building, Level 5, in the Department of Obstetrics and Gynecology. Subjects will be cared for in exam rooms typically used for delivering clinical care of patients in the FPMRS division.

25.0 Resources Available

Fifteen subjects will participate in this study, and participation will be limited to one visit on the day of enrollment. The identified study site sees an average of 50 patients per month for routine pessary care of which 80% are using a ring style or Gellhorn pessary and would be eligible to participate. Assuming 1:8 patients who is eligible agrees to participate, it should take 3 months to recruit patients and complete this study.

The Dartmouth-Hitchcock Clinic encompasses Dartmouth-Hitchcock Medical Center, a 381-bed hospital and the primary teaching hospital associated with the Geisel School of Medicine at Dartmouth. Outpatient care for patients seen in the Division of Female Pelvic Medicine and Reconstructive Surgery is provided on the 5th floor of the adjoining Faulkner Ambulatory Building. The clinic is a shared space with the Department of Obstetrics and Gynecology with a dedicated entrance, registration, and scheduling desk. Within the shared departmental clinical space, there are 30 exam rooms and 3 consult rooms in addition to two shared workrooms for provider documentation. Annually, there are over 2000 new patients seen at Dartmouth-Hitchcock with the diagnosis of pelvic organ prolapse (POP), and approximately 250 visits for new pessary fittings. The Dartmouth-Hitchcock Clinic utilizes an EPIC electronic medical record charting system

and has an electronic data warehouse which is searchable by diagnosis, procedures, and visit type.

The members of the study team are a cohesive group of practitioners who work together at The Dartmouth-Hitchcock Clinic providing clinical care. The study team will include five practitioners who have patients regularly scheduled for care in the study site and who will be available to provide medical treatment, should subjects develop an illness or injury because of their participation in the research study.

The investigator team and sponsor will meet as a group to review the consent form, protocol, instructions for use, data collection form, and phone script prior to commencing the study. Each member of the team will have adequate time to review the documentation and the opportunity to ask questions to the sponsor and principal investigator. During this meeting, the principal investigator will also assign duties and functions to each member of the team.

Early Feasibility Prospective Open-Label Study to Assess the Function of a Novel Pessary for the Non-Surgical Management of Pelvic Organ Prolapse

Protocol Number:	CP-001
NCT Number:	NCT04275089
Sponsor:	Reia, LLC ("Reia")
	[name]
	[name]
Medical Monitor:	[name]
	[name]
	[name]
Principle Investigator:	[name]
Study Site:	Department of Obstetrics and Gynecology
	Dartmouth-Hitchcock Medical Center
	[name]
	[name]
	[contact]
	Direct phone number for office of the PI: [contact]
	24-hour [contact]
Document Date:	2/17/2020

Statistical Design and Power

Recognizing that formal statistical procedures and power analyses are not the main focus of an early feasibility trial for a medical device, a few points will be made about the choice of 15 subjects. As reported by Cundiff et al. (2007), of 57 women initially successfully fitted with the Gellhorn pessary, within a week 21 had to be refitted which is a short-term fitting failure rate of about 37%. A 95% confidence interval about this proportion using an exact binomial test ranges from 24% to 51%. We can record the number of short-term failures in our preliminary study and compare our rate to Cundiff et al. If 4 of 15 (27%) of our subjects or fewer have to be refit, we could reject the null hypothesis of a short-term failure rate of .51 or greater at p < .05. Or, from a power perspective, if our true short-term failure rate was 21% or lower, power would be .81 or higher to reject the null hypothesis that our true failure rate is 51% or greater. This would give us another perspective on how fitting our new pessary compares to fitting existing pessaries.

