12.0 Local Number of Subjects

15 subjects will be recruited for this study. Typical early feasibility studies for medical devices include 5-15 subjects. The upper bound was selected due to the variability of the presentation of prolapse (apical, anterior, or posterior, as well as degree of severity) to evaluate performance of the Reia Vaginal Pessary across a broader range of clinical presentations.

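### The SAP's cutoff of 4 refits in 15 has an exact one-sided p of .0506 against a failure rate of .51, so the stated p < .05 narrowly fails; the stated power of .81 belongs to that .0506-level rule

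*SAP*

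**What the plan says.** The SAP section Statistical Design and Power starts from a published study in which 21 of 57 women fitted with a Gellhorn pessary needed refitting within a week, about 37%. Of the interval around that rate it says: "A 95% confidence interval about this proportion using an exact binomial test ranges from 24% to 51" percent. The upper limit becomes the null value for this study.

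The rule and its level follow: "If 4 of 15 (27%) of our subjects or fewer have to be refit", then "we could reject the null hypothesis of a short-term failure rate of .51 or greater at p < .05". The power statement is "if our true short-term failure rate was 21% or lower, power would be .81 or higher", again to "reject the null hypothesis that our true failure rate is 51% or greater".

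No method is named for the test apart from the exact binomial given for the interval. The test is not called one-sided, although the wording of the null and of the rule implies it.

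The SAP offers these figures as background: "a few points will be made about the choice of 15 subjects". It closes with "This would give us another perspective on how fitting our new pessary compares to fitting existing pessaries".

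**The concern.** A rule based on a count out of 15 can take only a few significance levels, and the steps between them are wide. A cutoff either meets .05 or it does not, and moving it by one subject changes both level and power a good deal. The SAP attaches two properties to one cutoff, p < .05 and power of .81 at a true rate of 21%, and states both as facts.

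If 4 of 15 does not meet .05, the claim fails exactly at the boundary the SAP names. Should 4 subjects be refit, a report that took p < .05 from this text would be wrong when the exact tail probability is computed. If the cutoff were moved to meet .05, the stated power would no longer apply.

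**Working it through.** **Inputs, all from the SAP, Statistical Design and Power.** n = 15; rule X ≤ 4 refits; null rate p0 = .51 or greater; alternative p1 = .21; historical data 21/57; named method exact binomial.

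**Formula.** P(X ≤ c | n, p) = Σ from k = 0 to c of C(n, k) p^k (1 − p)^(n − k). Because the null is .51 or greater and rejection is for low counts, the level is this lower tail at p = .51. Power is the same sum at p = .21.

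**Step 1: reproduce the SAP's interval.** The exact 95% interval for 21/57 (36.8%) is 24.4% to 50.7%, which rounds to the stated 24% to 51%.

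**Step 2: reproduce the SAP's power.** With n = 15 and p = .21, the terms for k = 0 to 4 are .0291, .1162, .2162, .2490 and .1986. They sum to .809, the stated .81. A normal approximation gives .798 and an arcsine approximation .796, both of which round to .80. The SAP's own figure therefore points to an exact calculation of the 4-of-15 rule.

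**Step 3: the level of that rule.** With n = 15 and p = .51:

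| k | P(X = k) |
|---|---|
| 0 | .00002 |
| 1 | .00035 |
| 2 | .00256 |
| 3 | .01156 |
| 4 | .03611 |
| Sum, 0 to 3 | .0145 |
| Sum, 0 to 4 | .0506 |

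The level is .0506, above .05 by .0006.

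**Step 4: sensitivity of the level.**
- With the unrounded upper limit, .5066, as the null, the tail is .0535.
- The tail falls to .05 only at a null of about .511.
- The two-sided exact p at .51 is .072.

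The one-sided test at the rounded value .51 is thus the most favourable of these exact readings, and it still misses.

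**Step 5: the next cutoff down.**

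| Rule | Exact one-sided level at .51 | Power at 21% | Power at 15% |
|---|---|---|---|
| 4 or fewer of 15 | .0506 | .809 | – |
| 3 or fewer of 15 | .0145 | .610 | .823 |

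The 3-of-15 rule reaches power .81 only at a true rate of about 15.4%. No fixed cutoff with 15 subjects has both exact p < .05 against .51 and power .81 at 21%.

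**The case against.** The strongest objection is that this is a rounding slip of no practical weight. The SAP gives its rates and its power to two decimals, and .0506 rounds to .05; the author may have written a strict inequality where an approximate one was meant. The SAP itself says that formal procedures and power are not the main focus. Refit rate is not among the endpoints in Protocol section 4.0. Section 12.0 supports the sample size independently: "Typical early feasibility studies for medical devices include 5-15 subjects". All of this stands, and it is why the point is minor. It does not make the inequality true.

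A second objection is that the SAP attaches the exact binomial to the interval and not expressly to the test. For 4 of 15 against .51, an uncorrected one-sided score test gives .030, a mid-p calculation .033 and a one-sided Wald test .017, all below .05; the continuity-corrected score test gives .052 and also fails. The error therefore depends on the exact method. But the SAP names none of the alternatives, and its power figure matches the exact calculation better than the approximations do. If another method was intended, the SAP needs to name it, so an edit is due either way.

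Third, the fall in power to .61 comes from the discreteness of 15 observations and overstates what .0006 is worth. That is fair. A randomised test that always rejects at 3 or fewer, and at 4 with probability (.05 − .0145)/.0361 = .983, would have power .610 + .983 × .1986 = .806. Nobody would run such a test here, but it shows that the excess level buys about .003 of power. This argues for keeping 4 of 15 and correcting the stated level.

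Finally, the Protocol's Study Summary gives a sample size of 15-20, and the conflict is specific to 15: at 18 subjects, 5 or fewer has exact level .040 and power .84 at 21%. But 15 is the number the SAP uses for its claim.

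**Conclusion.** The concern holds. Under a one-sided exact binomial test, 4 or fewer refits in 15 gives p = .0506 against a failure rate of .51, so the SAP's strict p < .05 is not met. Its power of .81 is correct for that rule, and so belongs to a test of level .0506. The conclusion rests on two assumptions: that the exact binomial named for the interval also governs the test, and that the test is one-sided. Both are well supported by the SAP's figures and wording, though neither is stated for the test. The severity is minor: a miss of .0006 in an ancillary comparison, with no effect on the endpoints or on the protocol's own case for 15 subjects.

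**What to change.** State in the SAP that the test is one-sided and exact binomial, then choose one of two wordings.

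- **(a) Keep 4 of 15.** Write that this rule has a one-sided exact level of .051 against a failure rate of .51, with power .81 at a true rate of 21%.
- **(b) Use 3 of 15 (20%).** Write that this rule has a one-sided exact level of .015, with power .61 at a true rate of 21% and .82 at 15%.

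Option (a) is preferable. It keeps the rule and the power figure and suits an ancillary comparison; its only cost is that the level reads .051 in place of < .05. Option (b) keeps the level strictly below .05 but gives up about 20 points of stated power at 21% (.81 − .61). Either takes two sentences of SAP text and changes nothing in enrolment, endpoints or procedures.
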